## TITLE COLLAPSIBLE PESSARY FEASIBILITY TRIAL STATISTICAL ANALYSIS PLAN

**13.0 PROPENSITY & FREQUENCY OF SELF-MANAGEMENT (SECONDARY)**

- 13.1 Endpoint
  - 13.1.1 Change in frequency of pessary removal for self-managers
  - 13.1.2 Change in management style (self-managed or exclusively practitioner-managed)
- 13.2 Data collection method
  - 13.2.1 At visit 0, the subject is asked to estimate the average number times per month their current pessary was removed/reinserted since their last visit.
  - 13.2.2 At visit 1 and visit 3, the subject is asked to estimate the number of times the pessary (current or study) was removed/reinserted since the last visit.
  - 13.2.3 During the visit 2 screen and at visit 2 if it occurs, the subject is asked to estimate the number of times the study pessary was removed/reinserted since visit 1.
- 13.3 Analysis group
  - 13.3.1 Current pessary self-management frequency will be estimated at visit 0 from the subject's memory, while the number self-management events with current pessary between visits will be reported at visit 1. Therefore, only visit 1 data will be used in the frequency analysis of the current pessary.
  - 13.3.2 Since visit 2 occurs 1-3 weeks after visit 1, time between visits is not sufficient to capture self-management. Therefore, visit 2 screen data and visit 2 in-person data will not be included in the frequency analysis. Instead, number of self-management events reported at visit 3, which occurs 11-13 weeks following visit 2, will be used in the analysis of the study pessary.
  - 13.3.3 Since data from visit 3 is required in the frequency analysis, only subjects who complete the study will be included in the analysis group.
  - 13.3.4 Visit 0 and visit 1 data will be used in the management style analysis for the current pessary. Visit 2 and visit 3 data will be used in the management style analysis for the study pessary.
- 13.4 Data analysis plan
  - 13.4.1 For visit 1 and 3 responses, number of self-management events since last visit will be converted to number of self-management events per month (defined as 28 days) using the number of days that passed between visits.
  - 13.4.2 For each subject, a difference (current pessary – study pessary) in number of self-management events per month will be calculated.
  - 13.4.3 A count of subjects who self-manage (number of self-management events per month > 0) will be calculated for the current pessary (visit 0 or 1) and the study pessary (visit 2 or 3).
  - 13.4.4 In the case that the rate data is not normally distributed as required by the t-test, we may transform the data, so it is reasonably normally distributed (using transformations such as the log or square root). If transforming the data does not result in a normal distribution, a non-parametric t-test may be used.
- 13.5 Reportable outcomes
  - 13.5.1 Average and standard deviation of the frequency of self-management with current and study pessary will be reported.

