	Pelvic Floor Impact Questionnaire (PFIQ- 7)	Between enrollment and the end of washout	Pelvic Floor Impact Questionnaire -7 is a health-related quality of life instrument, designed to assess the life impact of pelvic floor symptoms in women with pelvic floor disorders. The PFIQ-7 has a parallel structure to the PFDI with 3 Scales: CRAIQ, POPIQ and IIQ.
Secondary	Pelvic Organ Prolapse/Urinary Incontinence Sexual	the end of washout	A validated evaluation tool which can be used clinically as well as in research for assessment of female

DEIA	DOCUMENT NUMBER	CP-002-01	r 03
KEIA		PAGE	8 of 23

TITLE COLLAPSIBLE PESSARY FEASIBILITY TRIAL PROTOCOL

	Questionnaire, IUGA- Revised (PISQ-IR)	[Week 0-4] and post treatment [Week 16]	sexual function (FSF) in women with female pelvic floor disorders.
	Objective assessment of the pessary's ability to support the prolapse	At enrollment [Week 0], during treatment [Week 3-5], and during treatment [Week 16]	POP-Q points Ba and Bp (measurements of prolapse) will be measured during physical exam, with the pessary in situ.
Secondary	Global assessment of study pessary satisfaction compared to current pessary	For current pessary at the end of washout period [Week 3-5]; For study pessary post treatment [Week 16]	Satisfaction will be assessed using a Visual Analog Scale (VAS) with a 10 cm linear continuum in which 0 represents no satisfaction and 10 represents complete satisfaction.
Secondary	Pain associated with study pessary insertion compared to current pessary	During treatment [Week 3-5], during treatment [Week 5-7], and post treatment [Week 16]	Pain will be assessed using a Visual Analog Scale (VAS) with a 10cm linear continuum in which 0 represents no pain and 10 represents worst pain.
	Pain associated with study pessary removal compared to current pessary	During treatment [Week 3-5], during treatment [Week 5-7], and post treatment [Week 16]	Pain will be assessed using a Visual Analog Scale (VAS) with a 10cm linear continuum in which 0 represents no pain and 10 represents worst pain.
Other	Proportion of subjects successfully fit with the study pessary	Post treatment [Week 16]	Proportion of subjects who were successfully fit with the study pessary.
Other	Change in frequency of pessary removal for self-managers	Post treatment [Week 16]	The monthly frequency of pessary self-removal during the washout period will be compared against monthly frequency of self-removal in the treatment phase.

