Visit 0 [research purposes] will involve screening, enrollment, consent, subject questionnaires, and chart abstraction for historical data and will take place during a regularly scheduled pessary maintenance visit. The current pessary size and type will be recorded, and it will be observed in situ for the presence of rotation and its ability to support prolapse by measuring the distance of the most dependent compartment of the subject's prolapse to the hymen (POP-Q points Ba and Bp), as well as the distance from the leading edge of the current pessary, if a Gellhorn, to the hymen. After removal of the current pessary, a baseline physical exam will be conducted to assess for pre-existing vaginal pathology (ecchymoses, abrasions, superficial cuts, erosions, granulation tissue, bleeding) or urinary retention associated with current pessary use. Other exam elements will include assessment of vulvovaginal atrophy, pelvic muscle strength, perineal descent, and POP-Q points GH (with strain) and TVL. After cleaning, the current pessary will be replaced, and each subject will begin the washout period where they continue use of their current pessary. Either at this first visit or during the washout period, each subject will complete the PFDI-20, PFIQ-7, and PISQ-R to establish baseline scores. Self-

managers will track the frequency of removals. If the current pessary cannot be reinserted, they will be treated according to standard of care.

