Visit 3 [research purposes] will occur at the conclusion of the 3-month (from Visit 1) treatment phase - a typical length of time between routine visits for patients who choose long term pessary management of their prolapse. It can be scheduled in a window between 11 and 13 weeks from Visit 1. When the subject returns for Visit 3, a physical exam will be repeated, as in previous visits, for comparative data. The study pessary will be observed in situ for the presence of rotation and its ability to support prolapse by measuring the distance of the most dependent compartment of the subject's prolapse to the hymen (Points Ba and Bp), as well as the distance from the leading edge of the study pessary to the hymen. A VAS will be used to assess discomfort with removal of the study pessary, discomfort with reinsertion of their current pessary, and their global satisfaction of the study pessary. The subject will have been instructed to return with their current pessary which was removed in Visit 1. If the subject's current pessary is not brought to the visit, they will be given a new pessary of the size and style of their current pessary. Each subject will complete the PFDI-20, PFIQ-7, and PISQ-R for a post treatment comparison. For self-managers, other data collected will include frequency of removal and a VAS for ease of study pessary insertion and removal.

Additional Visits: Subjects will be seen as necessary and adverse events will be managed according to standard of care. If the study pessary falls out after Visit 1, the subject may be seen at their convenience for reinsertion or resizing. If a study pessary cannot be fit and retained, the subject will be withdrawn from the study and their current pessary will be placed. If the subject's current pessary is not brought to the visit, they will be given a new pessary of the size and style of their current pessary.

Special Circumstances: If a subject dies between Visit 1 and Visit 3, an attempt will be made to contact the coroner to retrieve the study pessary. If the study pessary cannot be retrieved, a copy of the death certificate will be obtained.

The study pessary is the only device that will be used in this trial. There will be no placebo devices placed. The study pessary is not cleared by the FDA, and a rationale is provided for a non-significant risk device claim in the attached documents.

Data Collected

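### Self-removal frequency is ascertained unequally in the two phases (3–5 against 11–13 weeks of look-back), and the Protocol and SAP disagree on how it is counted

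*SAP*

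**What the plan says.** Protocol 4.0 defines the endpoint as a within-woman comparison: "The monthly frequency of pessary self-removal during the washout period will be compared against monthly frequency of self-removal in the treatment phase".

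The documents describe the count as follows.

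- **Washout, Protocol 6.0 (Visit 0).** Self-"managers will track the frequency of removals". No diary, log or form is named. Visit 1 is aimed at 3–5 weeks after Visit 0.
- **Treatment phase, Protocol 6.0 (Visits 1 and 3).** Visit 1 provides teaching on insertion and removal but no instruction to track. At Visit 3, "For self-managers, other data collected will include frequency of removal", with no statement of how it is obtained. Visit 3 falls 11–13 weeks after Visit 1.
- **Both phases, SAP 13.2.2.** One question serves Visits 1 and 3 alike: "the subject is asked to estimate the number of times the pessary (current or study) was removed/reinserted since the last visit".
- **Data used, SAP 13.3.1 and 13.3.2.** "Current pessary self-management frequency will be estimated at visit 0 from the subject's memory", whereas events between visits are reported at Visit 1. "Therefore, only visit 1 data will be used in the frequency analysis of the current pessary". Visit 2 counts are left out because 1–3 weeks is judged too short to capture self-management, and the study-pessary rate comes from Visit 3.
- **Analysis, SAP 13.4.1 and 13.5.4.** Counts are rescaled to 28 days using the days between visits. The mean paired difference is tested against zero with a two-tailed t-test.

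**The concern.** A paired difference is interpretable only if both members of the pair are measured alike. Here the one tracking instruction covers the current-pessary phase, and the study-pessary count looks back two to four times as far. If women forget, round or telescope more over three months than over one, the two rates carry different errors, and the t-test cannot tell that from a real change in behaviour.

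The SAP itself treats memory as a weakness, since it gives memory as the contrast when it sets Visit 0 aside. Protocol 6.0 describes three months as a typical gap between routine visits, and Protocol 17.0 says this population attends every 3–4 months. The Visit 0 look-back is thus likely to be about as long as the one relied on at Visit 3.

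At stake is one of the endpoints bearing on the device's rationale, which is easier removal and reinsertion. Removals that were never recorded cannot be recovered at analysis.

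**Working it through.** The documents give no sample size, SD, alpha or power for this endpoint, so there is no planned figure to reproduce.

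**1. Look-back ratio (Protocol windows).** Study-pessary look-back divided by washout look-back:
- smallest: 11/5 = 2.2
- nominal: 12/4 = 3.0
- largest: 13/3 = 4.3

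**2. What the last visit means at Visit 3.** Visit 2 is 1–3 weeks after Visit 1 and may be omitted. If it is attended and counts as the last visit, the Protocol windows give a look-back of 11 − 3 = 8 to 13 − 1 = 12 weeks. That is still longer than the washout. If the woman counts from one visit and the analyst divides by days from the other, the rate is wrong by a known factor:
- count since Visit 1 over days since Visit 2: up to 11/8 = 1.38
- count since Visit 2 over days since Visit 1: down to 8/11 = 0.73

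**3. A conflict in the windows.** SAP 13.3.2 places Visit 3 at 11–13 weeks after Visit 2. Taken literally, that is 11 + 1 = 12 to 13 + 3 = 16 weeks after Visit 1, against 11–13 in the Protocol.

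**4. Rescaling.** If the true rate is λ per 28 days on both pessaries and a net fraction u is missed at Visit 3 relative to Visit 1, the rescaled difference (current − study) is λ − λ(1 − u) = λu. The length of the interval cancels and u does not. Neither λ nor u is in the documents, so the values below are assumptions.

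| Assumed λ per 28 days | u = 10% | u = 20% | u = 30% |
|---|---|---|---|
| 4 | 0.4 | 0.8 | 1.2 |
| 8 | 0.8 | 1.6 | 2.4 |

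Net over-recall gives the same sizes with the opposite sign.

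**5. Effect on the t-test (illustrative simulation, no device effect, 20,000 runs).** Assumed: individual rates follow a gamma distribution with mean 4 per 28 days and shape 1; counts are Poisson over 4 and 12 weeks; washout capture is complete; two-sided alpha is 0.05. The numbers of self-managers are also assumed. The entries are the share of runs that falsely reject.

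| Self-managers | u = 0 | u = 10% | u = 20% | u = 30% |
|---|---|---|---|---|
| 12 | 4.4% | 6% | 14% | 28% |
| 20 | 4.8% | 9% | 28% | 55% |
| 30 | 4.9% | 13% | 42% | 77% |

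The u = 0 column is also the result when both phases are ascertained equally: the test is then close to its nominal level.

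**The case against.** The strongest reply is that SAP 13.2.2 puts the same question, with the same verb, at Visit 1 and Visit 3. On the SAP alone, both counts are estimates. A reader might infer from the Protocol that washout removals are logged as they happen, that the phases use different methods, and that recall error falls only on the study pessary. The documents do not support this. The washout sentence names no diary, nothing says that tracking stops at Visit 1, and the data collection form is a separate document that was not available for this review. Both counts can carry recall error.

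Three further points have weight. Visit 0 asks for an average per month, while Visits 1 and 3 ask for a count over a dated interval, so setting Visit 0 aside is not purely a judgement about memory. The exclusion of Visit 2 is explained, and one to three weeks on a new device may indeed be unrepresentative. Finally, every recall figure above is assumed.

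What these points leave standing is the unequal look-back. If the Protocol's tracking sentence governs, the methods may differ. If the SAP governs, the method is the same but the recall span differs two- to four-fold. On either reading the two sides are not measured alike, and the documents do not say which reading applies.

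**Conclusion.** The point holds as unequal and unclearly specified ascertainment. It rests on three facts in the documents: a tracking instruction for the washout only, a look-back of 3–5 against 11–13 weeks (8–12 if Visit 2 counts as the last visit), and a study-pessary rate that depends on an estimate over about three months after Visit 0 was set aside as remembered. The difference tested in SAP 13.5.4 can therefore mix device effect with differential recall error.

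The size is not established. The range of 0.4 to 2.4 removals per 28 days assumes 4–8 true removals and 10–30% net under-recall. The false-positive rates rest on an assumed model as well. A reader might also infer that the bias works against the device; the documents do not settle the direction.

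The importance is moderate. The endpoint is labelled Other in Protocol 4.0 and secondary in the SAP and has no success criterion. Neither primary endpoint is affected.

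**What to change.** - **Protocol 6.0.** Have every woman who self-removes, including any who begins on the study pessary, keep the same dated removal record from Visit 0 to Visit 3. Name the form.
- **SAP 13.2.2, 13.3.1, 13.3.2 and 13.4.1.** Compute both 28-day rates from that record over the actual dated intervals. Where the record is missing, use a recalled count only in a sensitivity analysis.
- **Reconcile the documents.** State whether counts are tracked or estimated, whether the Visit 3 window runs from Visit 1 or Visit 2, and what the period since the last visit covers when Visit 2 is attended. With dated entries, the numerator and denominator necessarily refer to the same days.

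The cost is a tally card or REDCap log continued for about three more months and a few sentences of text, with no extra visit or procedure. The downside is a small diary burden on self-managers. The change has to be made prospectively.

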## TITLE COLLAPSIBLE PESSARY FEASIBILITY TRIAL STATISTICAL ANALYSIS PLAN

- 13.5.2 Mean difference (current pessary – study pessary) in number of self-management events per month will be reported.
- 13.5.3 The number of self-managers with the current pessary and study pessary will be reported.
- 13.5.4 We will use a two-tailed t-test to test the null hypothesis that the mean difference score between baseline (current pessary) and study pessary in the frequency of self-management is zero. This test is equivalent to a matched samples t-test. The p-value will be reported.
- 13.5.5 We will use a two-tailed t-test to test the null hypothesis that the mean difference score between baseline (current pessary) and study pessary in the number of self-managers is zero. This test is equivalent to a matched samples t-test. The p-value will be reported.

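### SAP 13 gives management style no paired analysis set or denominator, and a zero at Visit 2 alone can class a withdrawn woman as practitioner-managed

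*SAP*

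**What the plan says.** SAP section 13 covers two outcomes: how often the pessary is removed, and whether a woman self-manages at all (management style, 13.1.2).

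For frequency, the analysis set is clear. SAP 13.3.2 drops Visit 2 with the reason "Since visit 2 occurs 1-3 weeks after visit 1, time between visits is not sufficient to capture self-management". SAP 13.3.3 then restricts to completers: "Since data from visit 3 is required in the frequency analysis, only subjects who complete the study will be included in the analysis group".

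For management style, 13.3.4 names only data sources: "Visit 0 and visit 1 data will be used in the management style analysis for the current pessary", and "Visit 2 and visit 3 data will be used in the management style analysis for the study pessary". Under 13.4.3 a woman is a self-manager if she has any removal at either visit of the pair (0 or 1 for the current pessary, 2 or 3 for the study pessary). No analysis set, denominator or missing-data rule follows.

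Two results are reported. SAP 13.5.3 says: "The number of self-managers with the current pessary and study pessary will be reported". SAP 13.5.5 tests whether the "mean difference score between baseline (current pessary) and study pessary in the number of self-managers is zero", using a two-tailed t-test described as matched.

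**The concern.** A woman who withdraws can distort the comparison in two ways.

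(a) She leaves during washout, or after Visit 1 with no Visit 2 contact. She has current-pessary data and can be counted there, but she can never be counted for the study pessary.

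(b) Her only study-pessary record is a zero at Visit 2. Read literally, 13.4.3 makes her practitioner-managed. If she self-managed her current pessary, she enters the matched test as a switch away from self-management. This includes women who were never successfully fit, whom protocol section 13.0 withdraws at the end of Visit 2. They had no opportunity to remove a study pessary.

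At stake is a result that readers will take as bearing on the device's purpose, since protocol section 3.0 says it was engineered for easier removal and reinsertion. Attrition could look like a loss of self-managers or hide a gain. The counts and the p-value could also rest on different women.

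**Working it through.** The documents give no sample size, power or expected value for this outcome, so there is no figure to reproduce.

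**Inputs from the documents.** At least 50 enrolled and at least 40 completing (protocol 6.0), so about 10 losses, or 10/50 = 20%. Visit 2 falls 1-3 weeks after Visit 1, and Visit 3 falls 11-13 weeks after Visit 1 (protocol 6.0). SAP 13.3.2 instead dates Visit 3 from Visit 2, which should be reconciled.

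**Assumed, not in the documents.** Share of women who self-manage: 0.3, 0.5, 0.7. Removals among self-managers: 1 or 4 per 28 days, Poisson.

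**Step 1. Who can be misclassified.** The rule is any removal at Visit 2 or Visit 3. For a woman with Visit 3 data, a Visit 2 report can only add a true positive. Only a woman with Visit 2 data and no Visit 3 data can be wrongly classed because of the short window.

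**Step 2. Raw counts, error (a).** Suppose all 50 women contribute to the current-pessary count and 40 to the study-pessary count, with no change in behaviour and full ascertainment. Expected counts are 50 x share and 40 x share.

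| Assumed share | Current (50) | Study (40) | Apparent change | Same 40 women |
|---|---|---|---|---|
| 0.3 | 15 | 12 | -3 | 12 v 12 |
| 0.5 | 25 | 20 | -5 | 20 v 20 |
| 0.7 | 35 | 28 | -7 | 28 v 28 |

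A gain can be hidden too. At a share of 0.5, a true gain of 5 among the 40 (20 to 25) would read 25 v 25.

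**Step 3. The Visit 2 window, error (b).** P(at least one removal) = 1 - exp(-rate x weeks/4).

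| Removals per 28 days | 1 week | 3 weeks | 12 weeks |
|---|---|---|---|
| 1 | 0.221 | 0.528 | 0.950 |
| 4 | 0.632 | 0.950 | about 1 |

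If all 10 losses fell between Visit 2 and Visit 3 and half the women self-manage, the expected number of false switches is 10 x 0.5 x (1 - P). That is 10 x 0.5 x 0.779 = 3.9 at one removal per 28 days and a 1-week window. It is 10 x 0.5 x 0.050 = 0.25 at four removals and a 3-week window. Women never fit are outside this model, because their Visit 2 value is zero by construction.

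Steps 2 and 3 draw on the same roughly 10 women, so their effects cannot be added.

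**Step 4. The matched test.** A woman with no study-pessary data forms no pair and creates no false switch. That changes only if missing is coded as not self-managing, and the SAP does not say how missing status is handled. With k false switches in n = 50 pairs and no genuine switches, t = sqrt[k(n - 1)/(n - k)]:

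- k = 3: t = sqrt(147/47) = 1.77, p = 0.083 (exact McNemar 0.25)
- k = 5: t = sqrt(245/45) = 2.33, p = 0.024 (exact McNemar 0.063)
- k = 7: t = sqrt(343/43) = 2.82, p = 0.007 (exact McNemar 0.016)

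A handful of false switches is therefore enough to move the reported p-value.

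**Step 5. Comparison with the rest of the SAP.** Prolapse support (9.3.2), satisfaction (10.3.1), pain (11.3.1) and ease of use (14.3.1) all require data on both pessaries for the comparison. Management style has no such rule.

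**The case against.** A reader might infer that the SAP takes study-pessary status from Visit 2 alone and so contradicts itself. It does not. Status comes from Visit 2 or Visit 3. A window too short to estimate a monthly rate can still show that a woman has removed her pessary. Visit 2 may even be needed: 13.2.2 asks at Visit 3 about removals since the last visit, so when Visit 2 takes place the Visit 3 answer may miss the first 1-3 weeks. This objection stands for positive Visit 2 reports. It does not rescue a Visit 2 zero without later data.

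A reader might also infer that the plan compares different women by design and that attrition must produce a loss. The documents do not support that either. The 13.5.5 test is within-woman, so women without study-pessary data drop out of it. Nothing states that washout withdrawals enter the 13.5.3 count. The completer restriction in 13.3.3 could be read as covering the whole section. Against that last reading, its stated reason is the frequency analysis, and 13.3.4 follows with different visits and no restriction. If completers were meant throughout, one sentence would say so.

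The outcome is also of limited weight. The protocol's endpoint table lists removal frequency and ease for self-managers but not management style, and the SAP sets no success criterion for it. This bears on severity, not on whether the gap exists.

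**Conclusion.** The point holds as a possible error confined to women who withdraw. As written, 13.3.4, 13.4.3 and 13.5.3 allow the number of self-managers to fall with no change in behaviour, and allow a Visit-2-only zero to enter the 13.5.5 test as a false switch. The apparent loss of 3 to 7 women is an upper-end illustration: it needs all 10 losses to count for the current pessary and none for the study pessary. The false switches from the short window range from 0.25 to 3.9 only if every loss falls after Visit 2 and half the women self-manage. Shares and removal rates are assumptions. Severity is minor to moderate, for an SAP-added secondary outcome with no success criterion.

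**What to change.** In SAP 13.3.4 and 13.4.3, compute both counts and the 13.5.5 test on one paired set: women with current-pessary data and an evaluable study-pessary status. Evaluable means Visit 3 data, or a reported removal at Visit 2. Treat a Visit 2 zero without Visit 3 data as not evaluable, and state that missing status is not coded as practitioner-managed. State also whether the Visit 2 screening call counts as Visit 2 data here, since 13.3.2 names it separately and 13.3.4 does not.

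In 13.5.3, report n/N for each pessary, the paired 2x2 table, and the number of non-evaluable women.

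Add a sensitivity analysis using Visit 3 only. The main set keeps positive Visit 2 reports from withdrawn women but not their zeros, which could slightly favour the study pessary.

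The cost is a few sentences and one small table. The main comparison loses a few Visit-2-only women, who remain visible in the non-evaluable count.
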